At all follow-up visits, subjects will have an interval history obtained, undergo a directed physical examination, and have repeat specimens collected for STI testing (based on the subject history and clinic protocols). At all follow-up visits, subjects will undergo phlebotomy for serological testing for syphilis and serum storage. At the Month 3, Month 6, Month 9, and Month 12 follow-up visits, consenting HIV-uninfected subjects will be tested for HIV infection using a 4th generation serological test for HIV. At Visit 1, study staff will swab consenting subjects' oral cavities and primary or secondary lesions (if lesions are present per Section 5.1); see Section 8.2.2.

Safety will be measured by subject report and physical examination (including vital signs: temperature, heart rate, respiration rate, and blood pressure; and genital, rectal, oral, skin, and lymph node examinations). All AEs (including solicited reactogenicity AEs and other unsolicited AEs) will be recorded through Month 1. Safety oversight will be provided by a

Data and Safety Monitoring Board (DSMB) and site Independent Safety Monitors (ISMs) as described in Section 9.6.

While sites will perform their own serological testing as needed for subject management, serological testing to determine study outcomes and serum banking will be performed at the Central Laboratory (University of Alabama at Birmingham).

The duration of the study for each subject will be 12 months. Enrollment is expected to be completed in 36 months. For additional details on study procedures/evaluations and study schedule by study visits, see Sections 7 and 8 and Appendix A.

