### **7.2.4 Visit 5 – Month 3 (Day 90 ± 21 days)**

- Medical history will be reviewed (including review of interval medical records and local laboratory results, if available) and updated as appropriate. If the local laboratory results indicate a need for retreatment for syphilis infection, the subject will receive treatment

---

according to the local clinic's standard protocols and will be withdrawn from the study per protocol Section 5.3.3.

- Interim sexual history since the last study visit will be collected. Specimens will be collected at sites of exposure for STI screening/diagnosis as indicated by local standard of care and subject history.
- A urine pregnancy test will be performed on all subjects of childbearing potential.
- All concomitant medications taken since the last study visit will be recorded on the appropriate data collection form. Previously recorded medications will be updated as appropriate.
- A targeted physical examination will be performed by a qualified study clinician (including vital signs: temperature, heart rate, respiration rate, and blood pressure; and genital, rectal, oral, skin, and lymph node examinations).
- HIV testing will be performed if the subject was previously noted to be HIV-uninfected. Clinicians will provide pre- and post-test counseling, treatment, and referrals per local standard of care.
- Blood will be collected for follow-up RPR tests and storage.
- Contact information will be reviewed, and the Month 6 visit will be scheduled.

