### 11.2 Sample Size Considerations

Sample size calculations were performed using PASS 2008 and SAS 9.4. The following parameters were used for determining the required sample size for the primary objective:

- 1:1 allocation ratio between one-dose and three-dose arms
- Test the difference in response rate between the one-dose and three-dose arms (Farrington-Manning test, unadjusted for HIV status)
- Null hypothesis response rate in one-dose arm: 0.688
- Null hypothesis response rate in three-dose arm: 0.788
- Alternative hypothesis response rate in both arms: 0.788
- One-sided 0.05 alpha level

To achieve 80% power for the primary noninferiority comparison, 420 evaluable subjects (210 in each treatment arm) are needed. It is assumed that 25% of subjects will be ineligible for the primary analysis, and so 560 enrolled subjects are needed to reach the target of 420 evaluable subjects.

The study is not powered to assess the secondary noninferiority comparisons in the HIV status subgroups. As an illustration, power calculations were performed to assess the power available for these subgroup analyses using a sample size of 420. The following parameters were used for the calculations:

- Test the difference in response rate between the one-dose and three-dose arms within each HIV status stratum.
- Null hypothesis response rate in one-dose arm: 0.738 (HIV-infected); 0.638 (HIV-uninfected)
- Null hypothesis response rate in three-dose arm: 0.838 (HIV-infected); 0.738 (HIV-uninfected)
- Alternative hypothesis response rate in both arms: 0.838 (HIV-infected); 0.738 (HIV-uninfected)
- One-sided 0.05 alpha level
- 280 evaluable subjects in the HIV-infected stratum (140 in one-dose arm, 140 in three-dose arm).
- 140 evaluable subjects in the HIV-uninfected stratum (70 in one-dose arm, 70 in three-dose arm).

The HIV-infected noninferiority comparison has 72% power, and the HIV-uninfected noninferiority comparison has 38% power.

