### 11.4.1 Analysis Populations

Intent-to-Treat (ITT) Population: This analysis population includes all randomized subjects.

Modified Intent-to-Treat (mITT) Population: This analysis population includes all randomized subjects who are eligible at the baseline visit and whose TPPA result is positive at the baseline visit and/or at Visit 5 (Month 3), if repeat testing was performed.

Safety Population: This analysis population includes all randomized subjects who received at least one dose of study treatment.

Evaluable Population: This analysis population includes all randomized subjects who are eligible at the baseline visit, have a known HIV status determined at or before the baseline visit, have positive TPPA results at the baseline visit and/or Visit 5 (Month 3) (if repeat testing was performed), received all assigned doses of BPG, have adequate RPR titer data available at baseline and applicable follow-up visit(s), and (for HIV-uninfected subjects only) HIV-uninfected status persists through applicable follow-up visit(s).

If a subject receives antibiotic(s) active against *T. pallidum* for reasons other than syphilis between enrollment and the applicable follow-up visit(s), the subject will be included in ITT analyses but excluded from Evaluable analyses. If a subject receives antibiotic(s) active against *T. pallidum* between enrollment and the applicable follow-up visit(s) due to local RPR testing results, the subject will be included in all analyses.

A blinded case review committee will review subjects' data to determine if treatment with drug(s) known to be active against *T. pallidum* for reasons other than syphilis infection excludes the subject from the Evaluable analysis population.

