### 11.4.4 Efficacy Analysis Plan

#### 11.4.4.1 Primary Efficacy Analysis

For the primary analysis, serological response to therapy by Month 6 will be defined as follows:

- 4-fold or greater decline in RPR titer by Month 6 compared to baseline, OR
- RPR-negative by Month 6 (i.e., seroreversion).

For the primary analysis, subjects who do not meet either of the above criteria by Month 6 will be classified as not experiencing serological response. If a subject has an observed serological response prior to meeting one of the Evaluable analysis population exclusion criteria, the subject will be included in the analyses as a responder. For subjects who have received BPG through the study and subsequently require retreatment for syphilis infection (i.e., per the local clinic's standard protocols), data collected following retreatment will not be used for analyses. Exploratory analyses of the primary outcome will consider alternative classifications of subjects (see Section 11.4.4.2).

For the comparison of efficacy of one dose versus three doses of BPG 2.4 MU, the number and proportion of subjects with serological response will be summarized overall and by treatment.

The point estimates for the treatment-specific proportions and difference in proportions as well as corresponding 95% confidence intervals will be reported. A hypothesis test will be conducted using the Farrington-Manning test at the 5% one-sided level of significance to formally compare the treatment arms. The primary analysis will be performed in the ITT analysis population and repeated as a secondary analysis in the mITT and the Evaluable analysis populations.

As the ITT analyses will include subjects who may not have adequate serological data to determine their response status for any reason, the response will need to be imputed. Multiple methods for imputation will be explored (e.g., Last Observation Carried Forward); details will be provided in the Statistical Analysis Plan.

As a secondary corroborative analysis, the Cochran-Mantel-Haenszel Chi-square test will be used to compare the two treatment arms with respect to response rate across HIV status subgroups (HIV-infected, HIV-uninfected). The Breslow-Day test for the homogeneity of odds ratios will be used to determine if the difference between the two treatment groups with respect to response rates varies by HIV status.

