#### **11.4.4.2 Secondary Efficacy Analysis**

The secondary efficacy analyses will be performed in the ITT and Evaluable analysis populations. For subjects who have received BPG through the study and subsequently require retreatment for syphilis infection (i.e., per the local clinic's standard protocols), data collected following retreatment will not be used for analyses.

For the comparison of efficacy of one dose versus three doses of BPG 2.4 MU by Month 6 in each of the HIV status subgroups, the number and proportion of subjects with serological response will be summarized overall and by treatment within each HIV status subgroup. The point estimates for the treatment-specific proportions and difference in proportions as well as corresponding 95% confidence intervals will be reported. For each HIV status subgroup, a hypothesis test will be conducted using the Farrington-Manning test at the 5% one-sided level of significance to formally compare the treatment arms.

The analyses comparing one dose versus three doses by Month 12, overall and within HIV status subgroups, will follow similarly to the above. In addition, geometric mean titers and fold declines from baseline will be summarized by time-point for each treatment group, overall and within HIV status subgroups.

For the comparison of compliance between the one dose and three dose groups, the number and proportion of subjects who receive all assigned doses within the assigned visit windows will be summarized overall and by treatment. The point estimates for the treatment-specific proportions and difference in proportions as well as corresponding 95% confidence intervals will be reported. A hypothesis test will be conducted using a Chi-square test at the 5% two-sided level of significance to formally compare the treatment arms.

Demographic, sexual history, and other characteristics of subjects will be presented overall and within HIV status subgroups at baseline and throughout follow-up. HIV status subgroups will be compared with respect to epidemiological characteristics using the Pearson Chi-square test for categorical measures and the t-test for independent samples or Wilcoxon rank sum test for continuous measures.

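### The Evaluable rule that HIV-negative status must persist drops only HIV seroconverters not yet seen to respond, an avoidable outcome-dependent exclusion in the secondary repeat of the overall comparison

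*Protocol*

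**What the plan says.** Section 11.4.1 gives a single Evaluable definition. Besides eligibility, treponemal test, dosing and RPR requirements, it has two HIV conditions. Subjects must "have a known HIV status determined at or before the baseline visit", and for those who are HIV-uninfected it is further required that "HIV-uninfected status persists through applicable follow-up visit(s". The mITT definition in the same section has neither condition.

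That Evaluable set has several uses:

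- **Overall comparison (11.4.4.1).** "The primary analysis will be performed in the ITT analysis population and repeated as a secondary analysis in the mITT and the Evaluable analysis populations". Section 11.2 describes the test as "Farrington-Manning test, unadjusted for HIV status".
- **HIV-stratified analyses (11.4.4.1).** A Cochran-Mantel-Haenszel (CMH) test is planned to "compare the two treatment arms with respect to response rate across HIV status subgroups (HIV-infected, HIV-uninfected", with a Breslow-Day test of homogeneity.
- **HIV subgroup comparisons (11.4.4.2).** "The secondary efficacy analyses will be performed in the ITT and Evaluable analysis populations".
- **Enrollment caps (5.3.1).** These count 280 HIV-infected and 140 HIV-uninfected subjects confirmed evaluable, by their HIV status at baseline.

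Section 11.4.4.1 also contains a retained-responder rule: a subject whose response was observed before an Evaluable exclusion criterion was met is analysed as a responder.

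**The concern.** Acquiring HIV during follow-up is a post-randomization event. The overall test has no HIV term, so it does not need that event as a reason to set aside an RPR outcome.

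The more important issue is how the clause combines with the retained-responder rule. Two subjects may seroconvert at the same time. The one who has already responded stays in as a success, while the one who has not is removed. Whether a seroconverter is analysed therefore depends on the outcome being analysed, and the seroconverters who remain are all responders.

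In a noninferiority trial, a mechanism that lifts both arms' response rates above one half also tends to pull them together. The Evaluable repeat is the complete-treatment check on an ITT result that partly depends on imputed responses, so it should not carry an avoidable tilt toward noninferiority.

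**Working it through.** **1. The protocol's own figures (11.2).** Inputs: response rate 0.788 in both arms under the alternative, margin 0.10, one-sided alpha 0.05, 210 per arm. The Farrington-Manning constrained null rates are 0.730 and 0.830.

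- Null standard error: √[(0.730×0.270 + 0.830×0.170)/210] ≈ 0.0401
- Alternative standard error: √[2×0.788×0.212/210] ≈ 0.0399
- Power: Φ[(0.10 − 1.645×0.0401)/0.0399] ≈ 80.3%
- The smallest size giving 80% power is 209 per arm (418), which agrees with the stated 420.
- Enrollment: 420/(1 − 0.25) = 560, as stated.
- Subgroup power: 72.4% at 140 per arm and 38.2% at 70 per arm, against 72% and 38% stated.

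All figures reproduce. The point rests on no numerical error.

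**2. Who the clause removes.** Combining 11.4.1 with 11.4.4.1 for a subject HIV-uninfected at baseline who seroconverts before Month 6:

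| Response seen before seroconversion? | Evaluable analysis |
|---|---|
| Yes | Included as responder |
| No | Excluded |

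No seroconverter enters the Evaluable set as a non-responder.

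**3. Effect on the rates.** Let p be an arm's true response rate and d the share of its non-responders dropped by the clause. The Evaluable rate becomes

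p′ = p / [1 − d(1 − p)].

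This exceeds p for any d > 0. The slope of p′ in p is (1 − d)/[1 − d(1 − p)]², approximately 1 − d(2p − 1) for small d. It is below 1 when p is above one half, so a given difference shrinks when d is equal in both arms.

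**4. Illustration at the null rates in 11.2** (0.788 three-dose, 0.688 one-dose, difference 10.0 points). The values of d are assumptions, because the documents give no seroconversion rate.

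| d, both arms | Three-dose | One-dose | Difference (points) |
|---|---|---|---|
| 1% | 0.788/0.99788 = 78.97% | 0.688/0.99688 = 69.02% | 9.95 |
| 5% | 0.788/0.9894 = 79.64% | 0.688/0.9844 = 69.89% | 9.75 |
| 10% | 0.788/0.9788 = 80.51% | 0.688/0.9688 = 71.02% | 9.49 |

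For scale, at d = 5% and 210 per arm the dropped subjects number 210×0.05×0.212 ≈ 2.2 and 210×0.05×0.312 ≈ 3.3, or 5.5 in total. All would have to come from the HIV-uninfected stratum, planned at 140 evaluable (5.5/140 ≈ 4%). So 5% of all non-responders is not a low assumption.

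In the HIV-uninfected stratum alone, with null rates 0.738 and 0.638 and d = 10%, the rates become 0.738/0.9738 = 75.79% and 0.638/0.9638 = 66.20%, a difference of about 9.6 points. This assumes that the retained-responder rule also applies to the subgroup tests; 11.4.4.2 does not restate it.

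**5. Limits of the illustration.** It treats every dropped subject as a Month 6 non-responder. Some would have responded later, so the actual effect of a given number of exclusions is smaller. If both arms respond equally (0.788), both shift alike and the difference stays at zero.

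**The case against.** The strongest defence is that HIV status is central to this trial. Sections 2.1 and 2.2 treat the effect of HIV on serological response as unresolved. Holding status fixed in a secondary, per-protocol-type population is therefore a coherent choice. One definition also keeps the overall Evaluable set equal to the sum of its HIV strata (280 + 140 = 420). That stands as an explanation of the clause. It does not require exclusion, because classification by baseline status also gives strata that sum to the whole.

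Several stronger readings are tempting, but the documents do not support them:

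- **That the HIV clauses serve no analytic purpose.** They serve the subgroup, CMH and Breslow-Day analyses and the enrollment caps. Only the overall comparison has no need of the persistence clause.
- **That the known-baseline-status clause is equally at fault.** It does not depend on a post-randomization event. Visit 1 includes an HIV test for anyone without a documented positive result, so few subjects should fail it.
- **That the trial loses power.** Section 11.2 already allows 25% to be ineligible without splitting the reasons, and seroconverters who responded earlier are kept. Subtracting seroconverters from 420 would risk counting losses twice and would ignore those retained.
- **That subjects who decline an HIV retest are lost.** No text counts an untested subject as failing the clause, and that handling can be left to the SAP.
- **That Sections 4 and 7 conflict.** Section 4 refers to testing consenting subjects, while 7.2.4 says "HIV testing will be performed if the subject was previously noted to be HIV-uninfected". These are compatible, since testing depends on consent.
- **That 5.3.1 already fixes baseline status for the subgroup analyses.** Its reference to baseline is in the cap rules; the sentence on classifying subjects for the subgroup objective gives no time point.

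**Conclusion.** The point holds in a narrow form and is minor. As written, the persistence clause and the retained-responder rule together create an outcome-dependent post-randomization exclusion in the secondary Evaluable repeat of the overall comparison. It raises the Evaluable response rates. With similar seroconversion in both arms and response rates above one half, it also moves a true difference slightly toward zero, which is anti-conservative for noninferiority.

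Over the assumed 1% to 10% of non-responders dropped, a 10.0-point difference becomes 9.95 to 9.49 points. The true size cannot be obtained from the documents. If seroconversion frequency or timing differed by arm, the bias could be larger or smaller, but nothing in the protocol suggests that it would differ.

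A reader might infer that the primary conclusion is at risk. It is not: the primary analysis includes all randomized subjects, and the mITT population has no HIV condition.

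**What to change.** In 11.4.1, remove the requirement that HIV-uninfected status persist from the Evaluable definition, at least for the overall comparison. State that HIV status at baseline determines classification for the subgroup, CMH and Breslow-Day analyses and for the 280/140 caps; the cap rules in 5.3.1 already use it. Report exclusion of HIV seroconverters as a sensitivity analysis, so that the question the clause was meant to address is still answered.

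Removing the clause for every use, rather than for the overall comparison alone, is simpler. It leaves one Evaluable set that still equals the sum of its HIV strata.

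The cost is a short text change and one extra sensitivity analysis, with no new data and no planned analysis lost. The HIV-uninfected subgroup would include a few subjects who acquire HIV during follow-up, and the sensitivity analysis would show whether they matter.

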### 11.4.2 Baseline Characteristics

Baseline and demographic characteristics will be summarized overall and by formulation. For both continuous and categorical variables, appropriate summary statistics will be applied. For continuous variables, descriptive statistics will include the number of non-missing values, mean, standard deviation, median, minimum, and maximum. For categorical variables, descriptive statistics will include counts and percentages per category.

### 11.4.3 Safety Analysis Plan

Safety evaluations will be based on the incidence, severity, and type of AEs and SAEs, as detailed in Section 9. In addition, the incidence of systemic reactions and local injection site reactions will be evaluated. Safety variables will be tabulated and presented for all subjects in the safety population, grouped by treatment.

Reactogenicity events will be analyzed by taking the most severe response over the follow-up period, dichotomizing into a binary variable (none versus mild, moderate, or severe) and using exact confidence intervals to summarize the reactogenicity rates. Tabular and graphical summaries of events will be presented for each solicited event, by type (local/systemic), severity (none, mild, moderate, severe), and time point post-dose. The proportion of subjects who experience a Jarisch-Herxheimer reaction will be summarized overall and by treatment. Logistic regression analyses may be used to determine the association of treatment with Jarisch-Herxheimer reaction after adjusting for HIV co-infection status and time point.

Unsolicited AEs and SAEs will be coded by MedDRA® for preferred term and system organ class. The rate and exact 95% confidence intervals of AEs and SAEs in aggregate, as well as by MedDRA® categories, will be computed. The number of SAEs will be reported by a detailed listing showing the type, MedDRA® coding, relevant dates (treatment dosing date(s) and SAE onset and resolution dates), severity, relatedness, and outcome for each event.

### 11.4.4 Efficacy Analysis Plan

#### 11.4.4.1 Primary Efficacy Analysis

For the primary analysis, serological response to therapy by Month 6 will be defined as follows:

- 4-fold or greater decline in RPR titer by Month 6 compared to baseline, OR
- RPR-negative by Month 6 (i.e., seroreversion).

For the primary analysis, subjects who do not meet either of the above criteria by Month 6 will be classified as not experiencing serological response. If a subject has an observed serological response prior to meeting one of the Evaluable analysis population exclusion criteria, the subject will be included in the analyses as a responder. For subjects who have received BPG through the study and subsequently require retreatment for syphilis infection (i.e., per the local clinic's standard protocols), data collected following retreatment will not be used for analyses. Exploratory analyses of the primary outcome will consider alternative classifications of subjects (see Section 11.4.4.2).

For the comparison of efficacy of one dose versus three doses of BPG 2.4 MU, the number and proportion of subjects with serological response will be summarized overall and by treatment.

The point estimates for the treatment-specific proportions and difference in proportions as well as corresponding 95% confidence intervals will be reported. A hypothesis test will be conducted using the Farrington-Manning test at the 5% one-sided level of significance to formally compare the treatment arms. The primary analysis will be performed in the ITT analysis population and repeated as a secondary analysis in the mITT and the Evaluable analysis populations.

As the ITT analyses will include subjects who may not have adequate serological data to determine their response status for any reason, the response will need to be imputed. Multiple methods for imputation will be explored (e.g., Last Observation Carried Forward); details will be provided in the Statistical Analysis Plan.

As a secondary corroborative analysis, the Cochran-Mantel-Haenszel Chi-square test will be used to compare the two treatment arms with respect to response rate across HIV status subgroups (HIV-infected, HIV-uninfected). The Breslow-Day test for the homogeneity of odds ratios will be used to determine if the difference between the two treatment groups with respect to response rates varies by HIV status.

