## 11 STATISTICAL CONSIDERATIONS

### 11.1 Study Hypotheses

The primary objective of the study is to compare the serological response to therapy in subjects with early (primary, secondary, or early latent) syphilis treated with BPG 2.4 MU once or weekly for three successive weeks. In particular, the objective is to demonstrate noninferiority of the one-dose regimen compared to the three-dose regimen and to also assess noninferiority within the HIV status subgroups (HIV-infected and HIV-uninfected subjects). See Section 11.4.4 for the definition of serological response.

The null hypothesis for the primary objective is that the difference in serological response rate between the three-dose and one-dose groups is at least 10%, and the alternative hypothesis is that the difference in response rates is less than 10%. The null and alternative hypotheses for the secondary HIV status subgroup objective are defined similarly.

Note that tests will be performed and p-values will be reported for secondary analyses for informational purposes and not to make definitive claims. The study is intended and designed to formally test the primary hypothesis only, and so no corrections for multiplicity are planned.

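### Does a 95% interval beside a one-sided 5% noninferiority test leave the primary result ambiguous?

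*Protocol*

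**What the plan says.** Section 11.1 frames a noninferiority question with a 10-point margin: "The null hypothesis for the primary objective is that the difference in serological response rate between the three-dose and one-dose groups is at least 10" percent, and "the alternative hypothesis is that the difference in response rates is less than 10" percent. It adds that "The study is intended and designed to formally test the primary hypothesis only"; p-values for secondary analyses are informational.

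Section 11.2 sizes the trial for the Farrington-Manning test with the line "One-sided 0.05 alpha level". It arrives at 210 evaluable subjects per arm for 80% power, and with 25% loss "560 enrolled subjects are needed to reach the target of 420 evaluable subjects".

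Section 11.4.4.1 gives two consecutive statements. The first concerns estimation: for the arm-specific proportions and their "difference in proportions as well as corresponding 95% confidence intervals will be reported". The second concerns the decision: "A hypothesis test will be conducted using the Farrington-Manning test at the 5% one-sided level of significance", described as the formal comparison of the arms. The primary population is ITT.

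Section 11.4.4.2 repeats the pairing for the HIV subgroups and, by reference, for Month 12. For treatment compliance it puts the same estimation statement before a different test: "A hypothesis test will be conducted using a Chi-square test at the 5% two-sided level of significance".

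**The concern.** A noninferiority test and a confidence interval are usually read as two views of one calculation. A one-sided 5% test passes exactly when the two-sided 90% interval from the same statistic stays inside the margin. The margin-side limit of a two-sided 95% interval corresponds to one-sided 2.5%. The protocol therefore appears to look at the 10-point margin at two levels. Since the alternative hypothesis is itself a difference below 10 points, readers will hold the reported interval against that figure.

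If the interval decided noninferiority, the consequence would be serious. The working level would be one-sided 2.5%, power at 210 per arm would fall to about 71%, and 80% power would need 265 per arm (530 evaluable, 530/0.75 = 707 enrolled). If it were unclear which of the two decides, the choice could be made after the data are seen.

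**Working it through.** **Inputs (Sections 11.1, 11.2, 11.4.4.1).** Margin 0.10; response 0.788 in both arms under the alternative; 0.688 (one dose) against 0.788 (three doses) under the null; 1:1 allocation; one-sided alpha 0.05; power 80%; 420 evaluable, 560 enrolled. Assumptions made here: the 95% interval is two-sided, and for ITT all 560 are analyzed (280 per arm) with the rate still 0.788 after imputation. Differences are one-dose minus three-dose, so the margin lies at -10 points.

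**1. The plan's own sample size.** With the simple unpooled formula:

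n per arm = (1.645 + 0.842)² × 2 × 0.788 × 0.212 / 0.10² ≈ 207

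The asymptotic Farrington-Manning formula gives 209. Exact enumeration of the Farrington-Manning test at 210 per arm gives power 80.4%. Enrollment: 420/0.75 = 560. The stated figures reproduce at one-sided 5%.

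The illustrative subgroup powers do too. Asymptotic Farrington-Manning gives 72.4% (140 per arm, rate 0.838) and 38.2% (70 per arm, rate 0.738), against 72% and 38% stated. At one-sided 2.5% they would be 60.8% and 26.9%. The sizing section thus rests on one level throughout, and it is the level of the test in 11.4.4.1.

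**2. How often test and interval part.** The statistic is

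Z = (p̂₁ − p̂₃ + 0.10) / SE₀,

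with SE₀ computed under the restriction p₁ − p₃ = −0.10. The test passes if Z ≥ 1.645; the two-sided 95% score interval clears the margin if Z ≥ 1.960. Summing exact binomial probabilities over all outcome pairs:

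| | 280 per arm | 210 per arm |
|---|---|---|
| Test significant, 0.788 in both arms | 89.44% | 80.43% |
| 95% interval also clears the margin | 82.33% | 70.61% |
| Split (difference of the two) | 7.11% | 9.82% |
| Split as share of significant trials | about 8% | 12.2% |
| Split if the 95% interval is Wald | 6.85% | 9.27% |
| Test significant at the null boundary | 5.00% | 5.05% |

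If instead every one of the lost 25% counted as a non-responder, the rate would be 0.75 × 0.788 = 0.591 and the split at 280 per arm 9.6%.

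The split is always in one direction: Z ≥ 1.960 implies Z ≥ 1.645, so the score interval can never clear the margin when the test fails.

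**3. One such result.** Take 210/280 against 221/280, a difference of −3.93 points. The Farrington-Manning one-sided p is 0.044. The Wald standard error is √(0.750 × 0.250/280 + 0.789 × 0.211/280) ≈ 0.03555. The 90% limit is −3.93 − 1.645 × 3.555 = −9.78 points, and the 95% limit is −3.93 − 1.960 × 3.555 = −10.90 points. Score inversion gives the same two limits. The plan's verdict is noninferior, and the 95% interval shows that the result would not pass at one-sided 2.5%. Both statements are true.

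**4. What each statement is for.** In 11.4.4.1 the interval belongs to the reporting of estimates, for each arm and for the difference. The test is the stated means of formal comparison, at the level used in 11.2. No section says that noninferiority is concluded from an interval limit. The split in step 2 appears only when a reader uses the interval as a second test, which the protocol nowhere does.

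**The case for a change.** The best case for the concern is that this is not something left unsaid: the protocol itself fixes 95%. Reading that as a one-sided bound, which would agree with the test, is strained, because the same words cover the arm-specific proportions. The identical statement also stands before a two-sided 5% chi-square test in 11.4.4.2, where 95% does match, so it looks like stock wording used without regard to the kind of test. Nor does 11.4.4.1 call the interval descriptive. About 1 in 8 successful trials at 210 per arm would show the split, and one sentence would forestall the discussion.

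The arithmetic and the two-sided reading stand. What does not follow is that the result would be left open. Test, level, margin and interval level are all fixed before data, so a split is settled by the prespecified test and no choice remains to be made afterwards. Calling the 95% interval descriptive would only name the role it already has. A 90% interval could be added without harm, but Section 11.4 leaves the details of the analyses to a separate SAP, and 90% is the less conventional level to show.

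**Conclusion.** The concern does not hold. The hypotheses, the sample size and the primary test agree on a 10-point margin judged by Farrington-Manning at one-sided 5%; the planned size and power reproduce, and the error rate at the null boundary is 5.00% to 5.05%. A wider, conventional 95% interval reported for estimation is a legitimate choice on which statisticians differ.

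The split would occur in about 7% to 10% of trials under the design rates, depending on the number analyzed and the imputed ITT rate. That is a frequency of differing levels of evidence, not of error, and it alters no decision. The same holds for the HIV subgroup and Month 12 analyses, which 11.1 makes informational anyway.

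This rests on the test being the sole decision rule, as the protocol states. The SAP was not available to this review; the conclusion would change only if it made the 95% interval the basis for declaring noninferiority.
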